8.4 Compliance in Investigational Medicinal Product Administration

GWP42003-P is dispensed to the patient at visits as per the Schedule of Assessments in [Appendix 1](#). Further guidance on GWP42003-P dispensing will be provided in a separate pharmacy manual.

Caregivers will be asked to confirm dosing in the dosing schedule daily. Caregivers should return all GWP42003-P (used and unused) at each of the visits as per the Schedule of Assessments in [Appendix 1](#). The returned medication will be checked against the expected usage, and any discrepancies will be discussed with the caregiver at the time of the visit and documented accordingly within the patient's source documents. Caregivers will also be asked about the time of GWP42003-P administration in relation to meals.

The investigator must inform GW promptly of all missing or unaccountable GWP42003-P.

Records of GWP42003-P accountability will be maintained according to [Section 5.2.4](#).

8.5 Access to Blinded Treatment Assignment

This is not applicable.

Study Code: GWND19002
EudraCT Number: 2019-001605-24
Clinical Protocol V2 18Dec19

9 TRIAL PROCEDURES

A list of the required trial procedures is provided in the subsections that follow; refer also to the schedule of assessments ([Appendix 1](#)). Assessments or tests that are not done and examinations that are not conducted must be reported as such on the eCRF.

The location of the source data for the following procedures will be documented, per center, in a signed source data verification plan; for further details, see [Section 16.2](#).

9.1 Trial Procedures by Visit

Patients and their parent(s)/legal representative will be invited to take part in the trial and will be issued with the patient information and informed assent (if applicable) and the parent(s)/legal representative information and informed consent. Due to the degree of cognitive impairment in patients with RTT, patients 18 years of age or older will not be required to provide consent and will only be required to provide assent in cases where the patient possesses adequate understanding, along with parent(s)/legal representative consent. Following ample time to discuss the trial with the investigator, nurse, relatives, or caregiver, as wished, patients for whom the parent(s)/legal representatives provide written informed consent, and in cases where the patient possesses adequate understanding, patients who give their assent will be screened for entry into the trial. The nominated caregiver will be asked to consent to complete the QoL questionnaires.

Each visit should be scheduled to take place at approximately the same time of day (i.e., morning or afternoon), whenever possible. Visits 2, 3, and 16 (safety follow-up) are to be conducted by telephone.

The investigator should use his/her judgment and knowledge of the patient to determine when to best collect the blood and urine samples in order to mitigate the risk that invasive procedures may cause the patient to become stressed, thereby affecting the results of other patient assessments.

All assessments should reflect the patient's regular state, therefore it should be ensured the patient had adequate time to settle prior to each assessment. The CGI-S and CGI-I assessments should be based on the entirety of the visit.

Study Code: GWND19002
EudraCT Number: 2019-001605-24
Clinical Protocol V2 18Dec19

9.1.1 Clinic Visits

9.1.1.1 Visit 1 (Day 1)

Every effort should be made for this visit to take place on the same day as the RCT ‘End of Treatment’ visit. However, patients can still enter the OLE trial up to the point of the RCT follow-up (Visit 11).

OLE Visit 1 Assessments required for all patients:

- Informed consent and assent
- Eligibility check
- New medical history
- AE review
- GWP42003-P dispensing

OLE Visit 1 assessments required if OLE Visit 1 occurs on a different date than RCT Visit 9:

- Vital signs
- Hospital Services Use Questionnaire
- Suicidality assessment

OLE Visit 1 assessments required if OLE Visit 1 occurs > 28 days after RCT Visit 9:

- Physical examination (including weight)
- ECG
- Clinical laboratory blood sampling (hematology and biochemistry)
- Dipstick urinalysis (where possible)

Patients who satisfy all of the inclusion criteria and none of the exclusion criteria specified in [Section 6](#) will begin the treatment period.

Patients will be dispensed sufficient GWP42003-P and a dosing schedule for the following 3 weeks. Caregivers will be instructed on how to use the dosing schedule and how to measure and administer the medication. At the next visit, all GWP42003-P (used and unused) will be collected, and a check of the returned GWP42003-P against usage should be made.

Study Code: GWND19002

EudraCT Number: 2019-001605-24

Clinical Protocol V2 18Dec19

Based on [Section 9.1.3](#), assessments may be performed at unscheduled visits in the event of a safety concern, as deemed necessary by the investigator.

The investigator should review the laboratory results as soon as these become available.

If the results show a patient is ineligible, the patient will fail screening.

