9.1.1.2 Visit 4 (Day 29 [± 7])

A visit window of ± 7 days from the scheduled visit date is permitted, but it is preferred that the visit is performed on the scheduled visit day, where possible.

Information regarding changes to concomitant medications and AEs will be reviewed.

The investigator must assess adherence to the dosing schedule.

Vital sign assessments, physical examination (including body weight) and ECG assessments will be performed.

Clinical laboratory samples (urine [where possible] and blood) will be taken for hematology and biochemistry.

The caregiver will complete the RSBQ and Caregiver Assessment of Rett Symptoms.

The Hospital Services Use Questionnaire will be completed via interview.

The investigator will complete the CGI-S, CGI-I, and suicidality assessment.

All GWP42003-P (used and unused) will be collected, and a check of the returned GWP42003-P against usage should be made. Patients will receive sufficient GWP42003-P and a dosing schedule for the following 4 weeks.

Based on [Section 9.1.3](#), assessments may be performed at an unscheduled visit in the event of a safety concern, as deemed necessary by the investigator.

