The Hospital Services Use Questionnaire will be completed via interview.

The Tanner Stage will be recorded (where appropriate).

The investigator will complete MBA-9, CGI-S, CGI-I, and suicidality assessment.

The investigator must assess adherence to the dosing schedule. All GWP42003-P (used and unused) will be collected, and a check of the returned GWP42003-P against usage should be made. Patients will receive sufficient GWP42003-P and a dosing schedule for the period until the next scheduled Visit.

Based on [Section 9.1.3](#), assessments may be performed at an unscheduled visit in the event of a safety concern, as deemed necessary by the investigator.

Visit 14 only: Patients will receive sufficient GWP42003-P for the 10-day taper period, as applicable. For patients who discontinue GWP42003-P early, the taper period should start at the time the decision is made to discontinue, unless tapering the dose of GWP42003-P is inadvisable (e.g., continued dosing is not possible due to an AE). For patients who discontinue GWP42003-P early, the decision on whether or not to taper GWP42003-P will be left to the investigator's clinical judgment.

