9.2.10 Randomization and Trial Supply Management System

The RTSM system will be used to manage the IMP supply. The RTSM system information can be accessed via the eCRF.

A member of the trial team must register in the eCRF each clinic visit in order to:

- Obtain dispensing information (Visits 1, and 4 through 14 [end of treatment/withdrawal visit]).
- Provide completion/taper/early termination information (Visit 14/the end of treatment/withdrawal visit, or Visit 15 [end of taper], as applicable).

Training will be given to all centers prior to the start of the trial.

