9.2.11 Dosing Schedule/Compliance Review

Caregivers will be provided with a dosing schedule. Caregivers will be asked to confirm dosing in the dosing schedule daily from Visit 1 through Visit 15 (end of taper). Dosing compliance will be reviewed at each clinic visit. Any discrepancies will be discussed with the caregiver and documented accordingly within the patient's source documents.

Study Code: GWND19002
EudraCT Number: 2019-001605-24
Clinical Protocol V2 18Dec19

As part of the compliance review, caregivers will be asked at the visits about the time of GWP42003-P administration in relation to meals.

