9.2.14 Investigational Medicinal Product Accountability

Records of GWP42003-P accountability will be maintained according to [Section 5.2.4](#).

GWP42003-P will be dispensed at Visit 1 (Day 1) and every scheduled visit thereafter (Visit 4 through Visit 14 [end of treatment/withdrawal visit]).

Caregivers will be asked to return all GWP42003-P (used and unused) at each relevant visit (Visits 4 through Visit 15 [end of taper]). The center will check the returned GWP42003-P against the expected usage. Any discrepancies will be discussed with the caregiver at the time of the visit and documented accordingly within the patient's source documents.

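### Visit 1 supplies drug and a dosing schedule for 3 weeks, but the next dispensing visit is nominally 4 weeks later

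*Protocol*

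**What the plan says.** Protocol V2, section 9.1.1.1, states for Visit 1: "Patients will be dispensed sufficient GWP42003-P and a dosing schedule for the following 3 weeks".

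Section 9.2.14 sets the dispensing visits: "GWP42003-P will be dispensed at Visit 1 (Day 1) and every scheduled visit thereafter (Visit 4 through Visit 14". Section 9.2.10 (supply management system) and the dispensing row of Appendix 1 agree. No drug is therefore scheduled to be dispensed at Visit 2 (Day 8) or Visit 3 (Day 15). Section 9.1 adds: "Visits 2, 3, and 16 (safety follow-up) are to be conducted by telephone".

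Section 9.1.1.2 places Visit 4 on Day 29 with a window of 7 days either side and prefers the scheduled day. For that visit it requires: "The investigator must assess adherence to the dosing schedule". Section 9.2.11 and Appendix 1 footnote j have the caregiver complete the dosing schedule every day of the trial.

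For Visits 8, 10 and 14, section 9.1.1.6 gives no fixed number of weeks: "Patients will receive sufficient GWP42003-P and a dosing schedule for the period until the next scheduled Visit".

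**The concern.** The supply period at Visit 1 is shorter than the time to the next visit at which drug can be dispensed. It covers both the drug and the dosing schedule.

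A site that follows section 9.1.1.1 literally hands over a dosing schedule that stops a week before the nominal visit at which adherence to it is assessed. V2 does not describe issuing another one in between. The affected week falls during or just after titration, before Visit 4, which is the first scheduled on-treatment laboratory and ECG visit in a trial whose primary objective is safety.

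If dosing did lapse, the planned exposure summary would not show it. SAP section 6.1.8.4 counts dosing days as the last-dose date minus Day 1, plus 1, so an interruption before the last dose does not change the count.

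**Working it through.** **Inputs (Protocol V2).** Visit days are from Appendix 1 and supply periods from sections 9.1.1.1 to 9.1.1.9. Titration is from section 8.1.2: 5 mg/kg/day for a week, then weekly steps of 5 up to 15 mg/kg/day, with an option to go to 20. Strength is 100 mg/mL (section 5.1), in 100 mL bottles (section 5.2.1).

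**Interval against supply.** Interval = nominal day of the next visit minus nominal day of this visit. Supply = stated weeks × 7.

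| From – to | Interval (days) | Supply (days) | Shortfall (days) |
|---|---|---|---|
| Visit 1 – 4 | 29 − 1 = 28 | 3 × 7 = 21 | **7** |
| Visit 4 – 5 | 57 − 29 = 28 | 28 | 0 |
| Visit 5 – 6 | 85 − 57 = 28 | 28 | 0 |
| Visit 6 – 7 | 141 − 85 = 56 | 56 | 0 |
| Visit 7 – 8 | 197 − 141 = 56 | 56 | 0 |
| Visit 8 – 9 | 281 − 197 = 84 | to next visit | 0 |
| Visit 9 – 10 | 365 − 281 = 84 | 84 | 0 |
| Visit 10 – 11 | 456 − 365 = 91 | to next visit | 0 |
| Visit 11 – 12 | 547 − 456 = 91 | 91 | 0 |
| Visit 12 – 13 | 638 − 547 = 91 | 91 | 0 |
| Visit 13 – 14 | 729 − 638 = 91 | 91 | 0 |
| Visit 14 – 15 | 739 − 729 = 10 | 10 (taper) | 0 |

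Visit 1 is the only mismatch. Superseded Protocol V1 had the same 3 weeks while placing Visit 4 at 28 days after Visit 1, so the error was carried forward.

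**Visit window.** Visit 4 may fall on Days 22 to 36, which is 15 days. Three weeks covers Days 1 to 21 and so suffices only for a visit on Day 22 (1 of 15). The shortfall is 0 days at Day 22, 7 at Day 29 and 14 at Day 36. Four weeks covers Days 1 to 28 and suffices for Days 22 to 29 (8 of 15). Covering Day 36 takes 35 days, or 5 weeks.

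**Drug quantity, if exactly 21 days' worth is dispensed for full titration.**

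- Days 1 to 21: 7×5 + 7×10 + 7×15 = 210 mg/kg, or 2.10 mL/kg.
- Days 1 to 28, staying at 15 mg/kg/day: 210 + 7×15 = 315 mg/kg, or 3.15 mL/kg; 210/315 = 67%.
- Days 1 to 28, rising to 20 mg/kg/day on Day 22: 210 + 7×20 = 350 mg/kg; 210/350 = 60%.
- Days 1 to 28, stopping at 10 mg/kg/day: 7×5 + 21×10 = 245 mg/kg, still more than 210.
- Days 1 to 28, staying at 5 mg/kg/day: 28×5 = 140 mg/kg, less than 210, so no shortage.

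**Bottle rounding, if whole 100 mL bottles are dispensed** (an assumption; the pharmacy manual is not available). One bottle meets 21 days of full titration up to 100/2.10 = 47.6 kg and 28 days up to 100/3.15 = 31.7 kg. Up to 31.7 kg the 3-week wording leaves no drug shortage at the nominal Visit 4. Between 31.7 and 47.6 kg the count is one bottle for 3 weeks but two for 4. From 47.6 kg to 200/3.15 = 63.5 kg it is two either way.

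**The case against.** The mismatch itself is not disputable, and nothing in the documents corrects it. The case on the other side is that little follows from it.

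- **No quantity is fixed.** The protocol states no mg/kg amount and leaves dispensing detail to a pharmacy manual. Whole-bottle rounding could remove the drug shortage for many patients. This stands: 67% is a conditional figure, and no run-out is demonstrated.
- **The 20 mg/kg/day case is an extreme.** Section 8.1.2 expects a stable dose after titration, allows increases only if the investigator judges them necessary, and asks for discussion with the medical monitor. This stands; the 60% figure is an outer bound.
- **The window test is harsh.** Any supply equal to its nominal interval fails in the late half of the window, including the proposed 4 weeks. That is fair, but the other supply periods at least reach the nominal day and this one does not.
- **Other text requires daily completion of the dosing schedule throughout**, and staff assess adherence at the Day 8 and Day 15 calls. A sensible site would extend the schedule. That is plausible, but section 9.1.2.1 does not list issuing drug or a schedule at those calls, and bottle rounding cannot lengthen a schedule.
- **Detection exists.** Visit 4 checks returned drug against usage, so any loss of adherence information is partial. This stands.
- **The SAP dosing-day formula hides any interruption, whatever its cause.** True; it is context here and adds no separate weight.

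**Conclusion.** The point holds: section 9.1.1.1 is wrong as written. The shortfall is 7 days at the nominal Visit 4, ranging from 0 to 14 days across the permitted window, and it occurs at no other visit. This rests only on stated visit days and supply periods.

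The effect on the dosing schedule follows directly from a literal reading. The effect on drug does not. It depends on how much is actually dispensed, the titration rate, body weight and any rescue at the Day 15 call or an unscheduled visit, so the share of patients who would run short cannot be derived from the documents. No sample-size or inferential figure changes. The severity is minor.

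**What to change.** In section 9.1.1.1, replace 3 weeks with 4 weeks for both drug and dosing schedule, or use the wording of section 9.1.1.6 that supplies patients until the next scheduled visit. Align the pharmacy manual.

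The cost is a one-word correction and a check of the manual. Extra drug at Visit 1 is 315 − 210 = 105 mg/kg (1.05 mL/kg), or 350 − 210 = 140 mg/kg (1.40 mL/kg) if 20 mg/kg/day from Day 22 is allowed for.

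The text change helps only patients who have not yet had Visit 1. Annex 1 Amendment 1 states that screening for the lead-in trial is closed, and the SAP Overview states that the extension is being stopped prematurely. For patients already past Visit 1, review the Visit 4 accountability and dosing-schedule records for a gap between Day 22 and Visit 4.

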9.1.1.2 Visit 4 (Day 29 [± 7])

A visit window of ± 7 days from the scheduled visit date is permitted, but it is preferred that the visit is performed on the scheduled visit day, where possible.

Information regarding changes to concomitant medications and AEs will be reviewed.

The investigator must assess adherence to the dosing schedule.

Vital sign assessments, physical examination (including body weight) and ECG assessments will be performed.

Clinical laboratory samples (urine [where possible] and blood) will be taken for hematology and biochemistry.

The caregiver will complete the RSBQ and Caregiver Assessment of Rett Symptoms.

The Hospital Services Use Questionnaire will be completed via interview.

The investigator will complete the CGI-S, CGI-I, and suicidality assessment.

All GWP42003-P (used and unused) will be collected, and a check of the returned GWP42003-P against usage should be made. Patients will receive sufficient GWP42003-P and a dosing schedule for the following 4 weeks.

Based on [Section 9.1.3](#), assessments may be performed at an unscheduled visit in the event of a safety concern, as deemed necessary by the investigator.

9.1.1.3 Visit 5 (Day 57 [± 7])

A visit window of ± 7 days from the scheduled visit date is permitted, but it is preferred that the visit is performed on the scheduled visit day, where possible.

Information regarding changes to concomitant medications and AEs will be reviewed.

The investigator must assess adherence to the dosing schedule.

Vital sign assessments will be performed.

Clinical laboratory samples (urine [where possible] and blood) will be taken for hematology and biochemistry.

The caregiver will complete the RSBQ and Caregiver Assessment of Rett Symptoms.

Study Code: GWND19002
EudraCT Number: 2019-001605-24
Clinical Protocol V2 18Dec19

The Hospital Services Use Questionnaire will be conducted via interview.

The investigator will complete CGI-S, CGI-I, and suicidality assessment.

All GWP42003-P (used and unused) will be collected, and a check of the returned GWP42003-P against usage should be made. Patients will receive sufficient GWP42003-P and a dosing schedule for the following 4 weeks.

Based on [Section 9.1.3](#), assessments may be performed at an unscheduled visit in the event of a safety concern, as deemed necessary by the investigator.

9.1.1.4 Visit 6 (Day 85 [± 7])

A visit window of ± 7 days from the scheduled visit date is permitted, but it is preferred that the visit is performed on the scheduled visit day, where possible.

Information regarding changes to concomitant medications and AEs will be reviewed. The investigator must assess adherence to the dosing schedule.

Vital sign assessments, physical examination (including body weight) and ECG assessments will be performed.

Clinical laboratory samples (urine [where possible] and blood) will be taken for hematology and biochemistry.

The caregiver will complete the RSBQ, CSHQ and Caregiver Assessment of Rett Symptoms.

The Hospital Services Use Questionnaire will be completed via interview.

The investigator will complete MBA-9, CGI-S, CGI-I, and suicidality assessment.

All GWP42003-P (used and unused) will be collected, and a check of the returned GWP42003-P against usage should be made. Patients will receive sufficient GWP42003-P and a dosing schedule for the following 8 weeks.

Based on [Section 9.1.3](#), assessments may be performed at an unscheduled visit in the event of a safety concern, as deemed necessary by the investigator.

9.1.1.5 Visit 7 (Day 141 [± 7])

A visit window of ± 7 days from the scheduled visit date is permitted, but it is preferred that the visit is performed on the scheduled visit day, where possible.

Information regarding changes to concomitant medications and AEs will be reviewed. The investigator must assess adherence to the dosing schedule.

Study Code: GWND19002
EudraCT Number: 2019-001605-24
Clinical Protocol V2 18Dec19

Vital sign assessments will be performed.

Clinical laboratory samples (urine [where possible] and blood) will be taken for hematology and biochemistry for patients taking concomitant valproic acid, as well as for patients whose dose exceeds 15 mg/kg/day.

The caregiver will complete the RSBQ and Caregiver Assessment of Rett Symptoms.

The Hospital Services Use Questionnaire will be completed via interview.

The investigator will complete CGI-S, CGI-I, and suicidality assessment.

All GWP42003-P (used and unused) will be collected, and a check of the returned GWP42003-P against usage should be made. Patients will receive sufficient GWP42003-P and a dosing schedule for the following 8 weeks.

Based on [Section 9.1.3](#), assessments may be performed at an unscheduled visit in the event of a safety concern, as deemed necessary by the investigator.

9.1.1.6 Visit 8 (Day 197 [± 7]), Visit 10 (Day 365 [± 7]), and Visit 14 (Day 729 [± 7], End of Treatment/Withdrawal Visit)

A visit window of ± 7 days for Visits 8, 10, and 14 from the scheduled visit date is permitted, but it is preferred that the visit is performed on the scheduled visit day, where possible.

The patient should attend a withdrawal visit (Visit 14) as soon as possible after the decision is made to permanently discontinue GWP42003-P.

Information regarding changes to concomitant medications, AEs, and menstruation cycle (where applicable) will be reviewed. Vital sign assessments, physical examination (including body weight), height, and ECG assessments will be performed.

Clinical laboratory samples (urine [where possible] and blood) will be taken for the following:

- Hematology
- Biochemistry
- Dipstick urinalysis (provided urine can be obtained)
- Pregnancy test using a serum sample (as appropriate [[Section 9.2.2](#)])
- Determination of serum IGF-1 levels ([Section 9.2.9](#))

Study Code: GWND19002

EudraCT Number: 2019-001605-24

Clinical Protocol V2 18Dec19

The caregiver will complete the RSBQ, CSHQ, SF-36, CHQ-PF50, and Caregiver Assessment of Rett Symptoms.

The Hospital Services Use Questionnaire will be completed via interview.

The Tanner Stage will be recorded (where appropriate).

The investigator will complete MBA-9, CGI-S, CGI-I, and suicidality assessment.

The investigator must assess adherence to the dosing schedule. All GWP42003-P (used and unused) will be collected, and a check of the returned GWP42003-P against usage should be made. Patients will receive sufficient GWP42003-P and a dosing schedule for the period until the next scheduled Visit.

Based on [Section 9.1.3](#), assessments may be performed at an unscheduled visit in the event of a safety concern, as deemed necessary by the investigator.

Visit 14 only: Patients will receive sufficient GWP42003-P for the 10-day taper period, as applicable. For patients who discontinue GWP42003-P early, the taper period should start at the time the decision is made to discontinue, unless tapering the dose of GWP42003-P is inadvisable (e.g., continued dosing is not possible due to an AE). For patients who discontinue GWP42003-P early, the decision on whether or not to taper GWP42003-P will be left to the investigator's clinical judgment.

